13.1. Primary Objective #1 (Efficacy)

The first primary objective of this study is to demonstrate that the efficacy of Xpede™ Bone cement (Experimental group) is not inferior to the MENDEC (Control group) in terms of NRS score improvement at 6 months (24 weeks) postoperative from baseline.

13.1.1. Background

Considering that the VAS and the NRS are reproducible and comparable methods for measuring pain, the literature search was performed on the VAS. From a Systematic Review aimed to update the evidence base for Balloon Kyphoplasty (BKP) and Vertebroplasty (PV) in the management on patients with VCFs, the mean preoperative and postoperative VAS scores (standard deviations) were 8.36 (0.78) and 2.68 (1.09), respectively¹¹. In a population of osteoporotic fractures or vertebral metastasis after vertebroplasty the VAS mean (standard deviation) scores were 7.8 (1.2) before the procedure and 3.5 (1.3) at 6 months follow-up¹². Another paper based on the assessment of the treatment of spinal metastases, the pre-operative VAS mean (standard deviation) score was 6.85 (0.97), which decreased to 6 months 3.58 (1.63)¹³. From the KAVIAR study¹⁴ the estimated standard deviation for NRS is 3.27 (at 3 and 12 months visit).

13.1.2. Sample Size Calculations

Sample size calculations were performed in SAS software (SAS Institute Inc., Cary, NC, USA). A sample size is determined such that the non-inferiority of the primary objective is demonstrated that results are not appreciably worse in XPEDE arm compared to MENDEC Spine arm. Based on this information the assumptions for the sample size are:

¹¹ Gemma Marcucci, Maria Luisa Brandi. Kyphoplasty and vertebroplasty in the management of osteoporosis with subsequent vertebral compression fractures. Clinical Cases in Mineral and Bone Metabolism 2010; 7(1): 51-60

¹² Maiettini D., Orgera G., Bisaccia M., Piscitelli L., Laurino F., Meccariello L., Rebonato S., Schiaroli E., Rossi M. and Rebonato A.. Percutaneous Vertebroplasty Improves Pain Control and Quality of Life in Patients Suffering from Back Pain: A Single Center Experience.

¹³ Feng C., Yong-Hui X., Wen-Zhen C., Wei S., Yang G., Bo F. and Difei W. Percutaneous kyphoplasty for the treatment of spinal metastases. ONCOLOGY LETTERS 11: 1799-1806, 2016

¹⁴ Dohm M, Black CM, Dacre A, Tillman JB, Fueredi G; KAVIAR investigators. A randomized trial comparing balloon kyphoplasty and vertebroplasty for vertebral compression fractures due to osteoporosis. AJNR Am J Neuroradiol. 2014 Dec;35(12):2227-36.

- The NRS score which ranges from 0 to 10 is assumed to be approximately normally distributed.
- The NRS score is to be assessed at 24 weeks (6 months) after the procedure.
- The NRS at 24 weeks (6 months) is expected to be 3.5 in the MENDEC Spine treatment, and 3.5 or more in the Xpede. A difference in NRS score of 1.5 or less is considered clinically unimportant for this comparison¹⁵. It is considered the maximum acceptable increase in NRS score compared to the MENDEC Spine arm.
- The standard deviation of the NRS score is expected to be approximately 3.27 (the highest value from the literatures sited above) for each treatment. Common standard deviation will be assumed for both arms.
- The sample size should be sufficient to produce an 80% chance (power) of a significant result at a one-sided 0.025 significance level.

The non-inferiority margin "m" that characterizes the largest absolute difference considered to be dismissible is defined as 1.5. Since smaller values of NRS are better, the hypotheses are based on lower-tailed test:

$$H_0: \mu_X(t) \geq \mu_M(t) + m \quad \text{vs} \quad H_A: \mu_X(t) < \mu_M(t) + m$$

Where: t is 24 weeks (6 months), μ_X is the NRS mean score in the Xpede arm, μ_M is the NRS mean score in the MENDEC and "m" is the non-inferiority margin.

Based on this statistical test and assuming a one-sided type I error rate of 0.025 and a type II error rate of 0.20 or equivalently, power of 0.80 for the final analysis, it will be claimed that Xpede is not inferior to MENDEC with respect to NRS score if the upper bound of the two-sided 95% confidence interval of the difference ($\mu_X(t) - \mu_M(t)$) is less than the margin.

Thus, the non-inferiority hypothesis will require a sample size of 152 (76 per arm) subjects and including 15% of potential loss-to-follow-up, the total sample size for the study will be 179. If we use 3 * 3 * 2 strata, the sample size should be 180 to be divisible of 18 (90 per arm).

13.2. Primary Objective #2 (Efficacy)

The second primary objective of this study is to demonstrate that the efficacy of XPEDE bone cement (Experimental group) is not inferior to the MENDEC (Control group) in terms of Index Vertebral Body Angles **improvement** at 24 weeks (6 months) postoperative from baseline.

13.2.1. Background

In Cancer Patient Fracture Evaluation (CAFE) study¹⁶, the BKP patients' Index Spinal Deformity was measured by Index Vertebral Body Angles (VBA). The mean index VBA was 9.523 (8.751) at baseline and changed to 0.135 (5.088) and 0.954 (5.626) at respectively 1 month and 12 months .

¹⁵ Copay AG, Glassman SD, Subach BR, Berven S, Schuler TC, Carreon LY. Minimum clinically important difference in lumbar spine surgery patients: a choice of methods using the Oswestry Disability Index, Medical Outcomes Study questionnaire Short Form 36, and pain scales. Spine J. 2008 Nov-Dec;8(6):968-74

¹⁶ James Berenson, Robert Pflugmacher, Peter Jarzem, Jeffrey Zonder, Kenneth Schechtman, John B Tillman, Leonard Bastian, Talat Ashraf, Frank Vrionis, for the Cancer Patient Fracture Evaluation (CAFE) Investigators.

13.2.2. Sample Size Calculations

Sample size calculations were performed in SAS software (SAS Institute Inc., Cary, NC, USA). A sample size is determined such that the non-inferiority of the primary objective is demonstrated that results are not appreciably worse in XPEDE arm compared to MENDEC Spine arm. Based on this information the assumptions for the sample size are:

- The Angulation is assumed to be approximately normally distributed.
- The Angulation is to be assessed at 24 weeks (6 months) after the procedure.
- The Angulation at 24 weeks (6 months) is expected to be 1.2 in the MENDEC Spine treatment, and 1.2 or more in the XPEDE. A difference in Angulation of 2.5 or less is considered clinically unimportant for this comparison (half standard deviation rule). It is considered the maximum acceptable increase in Angulation compared to the MENDEC Spine arm. Standard deviation of 5.0 at 1 month from CAFÉ study was conservatively used to derive the non-inferiority margin of 2.5.
- The standard deviation of the Angulation is expected to be approximately 5.6 for both arms. Standard deviation of 5.6 at 12 months from CAFÉ study was conservatively used as the standard deviation for both arms.
- The sample size should be sufficient to produce an 80% chance (power) of a significant result at a one-sided 0.025 significance level.

The non-inferiority margin "m" that characterizes the largest absolute difference considered to be dismissible is defined as 2.5. Since smaller values of Angulation are better, the hypotheses are based on lower-tailed test:

$$H_0: \mu_X(t) \geq \mu_M(t) + m \quad \text{vs} \quad H_A: \mu_X(t) < \mu_M(t) + m$$

Where: t is 24 weeks (6 months), μ_X is the mean of index VBA I in the XPEDE arm, μ_M is the mean of index VBA in the MENDEC and "m" is the non-inferiority margin.

Based on this statistical test and assuming a one-sided type I error rate of 0.025 and a type II error rate of 0.20 or equivalently, power of 0.80 for the final analysis, it will be claimed that XPEDE is not inferior to MENDEC with respect to Angulation if the upper bound of the two-sided 95% confidence interval of the difference ($\mu_X(t) - \mu_M(t)$) is less than the margin. Thus, the non-inferiority hypothesis will require a sample size of 160 levels treated and including 20% of potential loss-to-follow-up, the total sample size for the study will be 200 levels treated (100 per arm). Using the same distribution of treated levels from FREE trial: 72% with 1 level, 21% with 2 levels, 7% with 3 levels, the required subjects will be $200/1.35 = 148$. If we use $3 * 3 * 2$ strata, the sample size should be 162 to be divisible of 18 (81 per arm), which is smaller than what is required for the first primary objective.

Balloon kyphoplasty versus non-surgical fracture management for treatment of painful vertebral body compression fractures in patients with cancer: a multicentre, randomised controlled trial. Lancet Oncol 2011; 12: 225–356

Medtronic Confidential

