5.2. Endpoints

5.2.1. Primary Endpoint(s)

The primary endpoints are as follows:

- Change of NRS score at 6 months postoperative from baseline .
- Change of Index Vertebral Body Angles 6 months postoperative from baseline

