- 2) Midline height (Hm) is obtained by placing a vertical line along the midline of the vertebral body from the midpoint of the superior vertebral body endplate to the midpoint of the inferior endplate. The height will be measured between the two opposing endplates. If the vertebra is tilted or image obliquely giving a double endplate appearance in the radiograph, the vertical midpoint of the intact endplate lines will be used as the reference point for measurement.
- 3) Anterior height (Ha) is obtained by placing a vertical line along the ventral surface of the vertebral body from the anterior point of the superior vertebral body endplate to the anterior point of the inferior endplate.

[figure not shown]

Figure 3: Vertebral Body Height

[figure not shown]

Figure 4: Examples of Using the Next Adjacent Non-Fractured Vertebra(e)

Magnification Adjustment

Vertebral Body Height will be adjusted for variation in image scale by the use of a magnification marker. The clinical sites are responsible for ensuring the use of magnification markers, provided by Medtronic, on all lateral images. Image readers will measure the diameter of the marker and the

Medtronic Confidential

ratio of the measurement diameter to the true diameter will define the magnification of the image. This magnification will be used to adjust all vertebral body height measurements to a common scale at each visit. If the marker is not present or not measurable at a particular visit, the reviewer may use a stable anatomical feature common with a calibrated visit to make a similar adjustment for scale differences.

B. Vertebral Body Angle

Vertebral body Angle should be assessed at Pre-Operative, 1 days, 3-, 6-month.

- 1) Two lines will be drawn, the first line along the superior endplate of the fractured vertebral body and the second line along the inferior endplate of the fractured vertebral body for each fractured vertebral body.
- 2) The angle between these two lines will then be measured. This is shown in Figure 5. Negative angles will be associated with a kyphosis (wedge-shaped) vertebral body; positive angles will be associated with lordotic (fish-mouthed) vertebral body. A zero-degree angle will indicate that the vertebral endplates are parallel.

[figure not shown]

Figure 5: Example of Measuring Vertebral Body Angle of a Treated Vertebra Vertebral Body Angle of Index Fracture

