13.4. Analysis of Clinical Data

Patient demographics and baseline characteristics will be presented using appropriate summary statistics. This includes mean and standard deviation, minimum, maximum and median with the interquartile range [IQR] for continuous variables, and counts and percentages for categorical variables. Summary statistics will be reported with maximum 2 decimals, as appropriate. The SAS software (SAS Institute Inc., Cary, NC, USA) or any other validated Statistical Software will be used to perform statistical analyses. The test for a treatment effect corresponds to showing that the upper bound of the two-sided 95% confidence interval (equivalent to the lower bound of a one-sided 97.5% confidence interval) for $\mu_E(t) - \mu_C(t) < \text{margin}$. Graphical representations will be used as deemed appropriate. No adjustments for multiple comparisons or multiple look at data will be performed. Outliers and influential observations will be identified via graphical plots and according to study team decision and the analysis could be repeated excluding potential outliers. In case of missing data, the imputation of missing data will be performed using the most appropriate method depending on the pattern of missing in the data and the type of the imputed variable. After the imputation of the missing values the models will be rerun.

The data will be analyzed according to the intention-to-treat principle and a Full Analysis Set (FAS) will be used for primary final analysis. The FAS is the patient set containing all the patients included in the study that have signed the study Informed Consent and have received the study treatment. A secondary analysis could be performed on a Per Protocol Set (PPS). The PPS patients set containing all the patients that meet the inclusion/exclusion criteria with no other major protocol deviation that

could impact the clinic outcomes and have the 6 months follow-up visits completed. Any patient who does not satisfy the inclusion/exclusion criteria or receives the wrong treatment will be eliminated from the per-protocol population. Details of endpoints analyses and additional analysis will be described in the Statistical Analysis Plan.

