The analysis on the second primary endpoint based on Index Vertebral Body Angles will use multiple data points per patient according to the number of levels treated. Assuming not completely independence among measures within same patient the analysis will be performed by means of Generalized Estimating Equation (or mixed models for repeated measures) using patient as the subject. The model will have the Index Vertebral Body Angles as dependent variables and baseline value, number of level treated (as the multiple data points) and arm as explanatory variables. All assumptions for regression models will be assessed by viewing plots of the residual values. It will be claimed that XPEDE is not inferior to MENDEC with respect to Angulation if the upper bound of the two-sided 95% confidence interval of the difference ($\mu_X(t) - \mu_M(t)$) is less than the margin.

The overall study is considered reached if both the null NI hypotheses are rejected. A separate Statistical Analysis Plan (SAP) will be developed prior to data being analyzed to further describe statistical methods, pre-specified data handling rules, and pre-specified analyses that will be included in the final study reports. Any deviation from the pre-specified statistical analyses will be noted in the study report.

The Statistical Analysis Plan will include a comprehensive description of the statistical methods and analyses to be included in reports that include analysis of endpoints. Any change to the data analysis methods described in the CIP will require an amendment only if it changes a principal feature of the CIP. Any other change to the data analysis methods described in the CIP, and the justification for making the change, will be described in the clinical study report.

14. Ethics

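### The vertebral body angle co-primary is recorded with kyphosis negative but tested as if smaller angles were better, so the plan read literally reverses the non-inferiority test

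*Protocol*

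**What the plan says.** **Measurement.** Protocol 9.8, part B, sets the sign of the recorded angle: "Negative angles will be associated with a kyphosis (wedge-shaped) vertebral body; positive angles will be associated with lordotic (fish-mouthed) vertebral body". Parallel endplates are zero. Protocol 9.9 and SAP 7.9.1.2 base the final conclusion on the independent readings.

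**Hypothesis.** Protocol 13.2.2 states: "Since smaller values of Angulation are better, the hypotheses are based on lower-tailed test". It calls 2.5 degrees the largest tolerable increase and takes as null hypothesis that the Xpede mean is at least the Mendec mean plus 2.5. SAP 6.2 repeats the margin and its direction.

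**Planning values.** Protocol 13.2.1 cites a kyphoplasty trial in cancer patients in which the mean angle was 9.523 at baseline and later 0.135 and 0.954. Protocol 13.2.2 adds: "The Angulation at 24 weeks (6 months) is expected to be 1.2 in the MENDEC Spine treatment".

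**Decision rule.** Protocol 13.4 gives a general rule: "The test for a treatment effect corresponds to showing that the upper bound of the two-sided 95% confidence interval" for the difference lies below the margin. It repeats this for VBA: "XPEDE is not inferior to MENDEC with respect to Angulation if the upper bound of the two-sided 95% confidence interval" is below the margin. SAP 7.9.1.2 writes the contrast as the Xpede 6-month mean minus the Mendec 6-month mean, against 2.5. The model has the angle as dependent variable and baseline as a covariate.

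**Endpoint name.** Protocol 5.2.1 calls it "Change of Index Vertebral Body Angles 6 months postoperative from baseline", and Protocol 13.2 speaks of improvement. Neither document gives the order of subtraction for VBA, although SAP 10.3.1 does so for vertebral height, a secondary endpoint.

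**The concern.** The two parts of the plan use opposite signs. Under 9.8, a vertebra that becomes more wedge-shaped moves to a smaller number. Under 13.2.2, a smaller number is better. A deformity that starts near +9.5 and falls towards zero after treatment fits deformity coded positive, which is not how 9.8 codes kyphosis.

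A programmer who takes the readings as recorded and applies the rule as written builds a test that tolerates extra kyphosis and penalises less kyphosis. Double programming, as in SAP section 8, checks that code matches its specification, so it need not catch an error in the specification itself.

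Because both co-primaries must succeed, a reversed VBA test can decide the trial either way. Fixing the sign after unblinding would leave the result open to challenge.

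**Working it through.** **Inputs.** Margin 2.5, SD 5.6, one-sided alpha 0.025, power 0.80, true difference 0, 160 levels before 20% loss (Protocol 13.2.2). Level mix 72/21/7% for 1, 2 or 3 levels (Protocol 12 and 13.2.2). Baseline correlation r and within-patient correlation ICC are not given; 0 to 0.5 is assumed for each.

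**The plan's own figure.** The normal approximation gives 79 levels per arm (158 in all); the noncentral t gives 80 per arm, the stated 160. Then 160/0.80 = 200 levels and 200/1.35 = 148 subjects, which rounds up to 162 as a multiple of 18. The sizing reproduces.

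**Pass probability.** Let d be the true Xpede minus Mendec difference on the 9.8 scale, so negative d means more kyphosis.

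- Written rule, angles unconverted: Φ((2.5 − d)/SE − 1.96).
- Rule and signs matched: Φ((2.5 + d)/SE − 1.96).
- SE = 5.6 × √(2/80) = 0.885, treating levels as independent, as the plan's sizing does.

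For 2.5 degrees more kyphosis (d = −2.5), the unconverted rule gives Φ(5/0.885 − 1.96) = Φ(3.69) = 0.9999. The matched rule gives Φ(−1.96) = 0.025.

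| Xpede truly leaves | d | Unconverted 9.8 signs | Signs matched |
|---|---|---|---|
| 2.5° more kyphosis | −2.5 | 0.9999 | 0.025 |
| 1° more | −1 | 0.977 | 0.395 |
| no difference | 0 | 0.806 | 0.806 |
| 1° less | +1 | 0.395 | 0.977 |
| 2.5° less | +2.5 | 0.025 | 0.9999 |

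**Range.** With baseline in the model, residual SD = 5.6 × √(1 − r²), which is 5.6 at r = 0 and 4.85 at r = 0.5. For clustering, mean levels per patient = 0.72 + 2(0.21) + 3(0.07) = 1.35 and mean squared levels = 0.72 + 4(0.21) + 9(0.07) = 2.19. The design effect is DE = 1 + (2.19/1.35 − 1) × ICC, and SE = SD × √(2·DE/n). Take n = 80 (planned) or 180 × 1.35 × 0.8/2 = 97 (expected from 180 patients). Unconverted results:

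| r | n per arm | ICC | SE | d = −2.5 | d = −1 | d = 0 | d = +1 |
|---|---|---|---|---|---|---|---|
| 0 | 80 | 0 | 0.885 | 0.9999 | 0.977 | 0.806 | 0.395 |
| 0 | 80 | 0.5 | 1.014 | 0.9985 | 0.932 | 0.694 | 0.315 |
| 0 | 97 | 0.5 | 0.921 | 0.9997 | 0.967 | 0.775 | 0.370 |
| 0.3 | 80 | 0 | 0.845 | >0.9999 | 0.986 | 0.841 | 0.427 |
| 0.5 | 97 | 0 | 0.696 | >0.9999 | 0.999 | 0.948 | 0.577 |

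With matched signs, the d = −2.5 figure is 0.025 in every row, and the d = −1 figure equals the d = +1 column.

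**Direction of change, by simulation.** Linear model with arm and baseline, 80 single levels per arm, baseline 9.523 (SD 8.751), 6-month 1.2 (SD 5.6), 10,000 trials per case, Xpede 2.5 degrees more kyphotic:

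| Dependent variable | Signs | Pass rate, r = 0 | Pass rate, r = 0.3 |
|---|---|---|---|
| 6-month value | 9.8, unconverted | 0.9999 | 0.9998 |
| 6-month minus baseline | 9.8, unconverted | 0.9999 | 0.9998 |
| Baseline minus 6-month | 9.8, unconverted | 0.0247 | 0.0259 |
| 6-month value or 6-month minus baseline | multiplied by −1 | 0.0247 | 0.0259 |

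The first two rows must agree, because baseline is a covariate; the second is not independent confirmation. The third shows that the opposite subtraction would put the rule right without any conversion.

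**The case against.** **The intent is clear.** Protocol 13 and SAP 6.2 and 7.9.1.2 consistently treat larger angles as worse; only 9.8 differs, and it is a reading instruction. An analyst might notice negative mean baseline angles. This is fair: 0.9999 is conditional on following both texts literally and is not a forecast. But the decisive readings are to be recorded under 9.8, and nothing readable tells the analyst to convert them.

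**The order of subtraction does not enter the written rule.** The rule contrasts 6-month means, with baseline as covariate. That is correct for the rule as worded, and makes this the weaker half of the point. It still needs settling, because the endpoint is named as a change and, in one place, an improvement, and one reading of change undoes the reversal.

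**A figure or separate document may settle it.** Protocol Figure 5, the figure in SAP 10.2, the table mock-ups and any core-lab instructions were not available. A conversion could be stated there, but 9.8 and 13.2.2 would still conflict.

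**An unadjusted change score gives smaller probabilities.** With baseline SD 8.751, the change SD is √(8.751² + 5.6²) = 10.39 at r = 0 and 7.68 at r = 0.5. The reversed pass probability at 2.5 degrees more kyphosis is then about 0.86 and 0.985. This arithmetic is right, but the plan's primary VBA model adjusts for baseline, and even 0.86 is far from 0.025.

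**Multiplying by −1 makes lordosis count as ever better.** So does the scale the plan already uses: a mean of 0.135 with SD 5.088 implies values on both sides of zero. The recoding restores that scale and adds no new problem, though the text should name kyphosis as the direction of harm.

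**Conclusion.** The concern holds. The recording convention and the decision rule for a co-primary endpoint have opposite signs, and no readable text reconciles them. If angles under 9.8 enter the rule unconverted, as 6-month values or 6-month minus baseline, a cement worse by exactly the margin passes with probability 0.9999 instead of 0.025. Over the assumed ranges of r, ICC and levels per arm, that figure is 0.9985 to above 0.9999. One degree more kyphosis passes with 0.932 to 0.999 instead of 0.315 to 0.577.

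These figures rest on the plan's SD and margin, approximate normality and the baseline-adjusted model. The sample size is unaffected, because at zero true difference the pass probability is the same in either direction. This must be fixed before unblinding.

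**What to change.** In SAP 7.9.1.2, state that site and core-lab angles recorded under Protocol 9.8 are multiplied by −1 before analysis, so that kyphosis is positive and is the direction of harm, and that change means 6-month minus baseline. Keep the rule that the upper 95% bound of Xpede minus Mendec must lie below +2.5. Cross-reference this in Protocol 9.8, 13.2.2 and 13.4, and apply the same coding to the secondary VBA changes in SAP 4.2 and 7.9.2.

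The alternative is to keep the 9.8 signs and require the lower 95% bound of Xpede minus Mendec to lie above −2.5. The planning value of 1.2, the statements on direction and the claim rules in Protocol 13.2.2 and 13.4 and SAP 6.2 and 7.9.1.2 would then all need re-signing. The cited values in Protocol 13.2.1 would have to be re-signed or given a coding note, and the general upper-bound rule in 13.4 would need an exception for VBA. The first option is simpler.

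The cost is one paragraph and a few cross-references, with no extra data, patients or resizing.

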7.9.1.2. Primary Endpoint on Vertebral Body Angles

The primary endpoint on Vertebral Body Angles (VBA) is the mean change of Index Vertebral Body Angles from baseline at 6 months in the subjects treated with Kyphon®Xpede™Bone Cement compared with subjects treated with Mendec Spine Bone Cement. It will be claimed that XPEDE is not inferior to MENDEC with respect to Vertebral Body Angles if the upper bound of the two-sided 95% confidence interval of the difference (Mean Vertebral Body Angles in the XPEDE arm at 6 months - Mean Vertebral Body Angles in the MENDEC arm at 6 months) < 2.5.

X-ray images will be reviewed by independent radiological reviewers who will be blinded to the subjects' treatment groups for each analysis. Adjudications provided both by the site and by the independent reviewers will be analyzed separately. Final conclusion will be made according to independent reviewer adjudication.

The analysis will be performed by means of Generalized Estimating Equation (or mixed models for repeated measures) using patient as the subject. The model will have the Index Vertebral Body Angles as dependent variables and baseline value, number of levels treated (as the multiple data points), type of procedure and arm as explanatory variables. All assumptions for regression models will be assessed by viewing plots of the residual values.

As sensitivity analysis, comparison will be also performed by t-test on:

1. the average value of VBA for the 3 separate treated levels;
2. the value of VBA for all the 3 pooled treated levels.

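### The vertebral-angle co-primary tests a signed mean in one direction on a scale that runs both ways from parallel, and no planned analysis summarises the absolute angle

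*Protocol*

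**What the plan says.** Protocol section 9.8, part B, defines the angle between the two endplates of each fractured vertebra: "Negative angles will be associated with a kyphosis (wedge-shaped) vertebral body; positive angles will be associated with lordotic (fish-mouthed) vertebral body". It adds: "A zero-degree angle will indicate that the vertebral endplates are parallel".

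Protocol section 13.2.2 plans the second co-primary on this angle. Its null hypothesis is that the Xpede mean is at least 2.5 degrees above the Mendec mean, and its stated reason for the direction is: "Since smaller values of Angulation are better, the hypotheses are based on lower-tailed test". The planning assumptions are:

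- "The Angulation at 24 weeks (6 months) is expected to be 1.2 in the MENDEC Spine treatment, and 1.2 or more in the XPEDE"
- "The standard deviation of the Angulation is expected to be approximately 5.6 for both arms"
- "The Angulation is assumed to be approximately normally distributed"

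Section 13.4 and SAP 7.9.1.2 keep the same rule: the upper limit of the two-sided 95% interval for the difference in signed means must fall below 2.5. There is no lower limit and no category for overshoot.

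SAP 7.9.1.2 then adds: "As sensitivity analysis, comparison will be also performed by t-test on" the averaged and the pooled treated levels. Both t-tests use the signed value, as does the secondary angle endpoint in SAP 7.9.2.

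**The concern.** A smaller-is-better rule suits a scale on which deformity lies on one side only. Here section 9.8 names a shape on each side of zero. If kyphosis is positive, a level already past parallel on the fish-mouth side is credited for going further. If kyphosis is negative, as section 9.8 says, a wedged level is credited for wedging further. Settling the sign decides which side is affected but does not remove the problem.

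The rule matters most when the mean is close to zero, where the plan expects it at 6 months. A signed mean near zero can come from vertebrae that are close to parallel, or from collapse in some levels offset by movement the other way in others. The co-primary cannot tell these apart, yet it is one of the two results that must both succeed for a registration claim of non-inferior angle improvement.

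**Working it through.** **Inputs.** The 6-month mean of 1.2, SD of 5.6, normality, 2.5-degree margin, one-sided 0.025 and 80% power come from protocol 13.2.2. The cited cancer-fracture trial's angles, from 13.2.1, are 9.523 (SD 8.751) at baseline, 0.135 (5.088) at 1 month and 0.954 (5.626) at 12 months.

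**The plan's own figure.** The normal approximation gives n per arm = 2 × (1.96 + 0.842)² × 5.6² / 2.5² = 78.8, so 79 per arm and 158 levels. The noncentral-t calculation gives 80 per arm, 160 levels, with power 0.801. Then 160/0.80 = 200 levels, 200/1.35 = 148 subjects, and the next multiple of 18 is 162. The plan's figures reproduce.

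**Share of levels below zero**, Φ(−mean/SD):

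| Source | Mean (SD) | Below zero |
|---|---|---|
| Cited baseline | 9.523 (8.751) | 13.8% |
| Planned 6 months, face value | 1.2 (5.6) | 41.5% |
| Cited 12 months | 0.954 (5.626) | 43.3% |
| Cited 1 month | 0.135 (5.088) | 48.9% |
| Planned 6 months, sign reversed | −1.2 (5.6) | 58.5% |

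The last row applies if the cited trial counts kyphosis as positive, as its baseline of +9.523 falling towards zero suggests. The planning mean would then have to be reversed to sit on the section 9.8 scale.

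At face value, the share more than 2.5 degrees below zero is Φ((−2.5 − 1.2)/5.6) = Φ(−0.661) = 25%. About 16 of the 42 percentage points are therefore overshoot no larger than 2.5 degrees.

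**Mean absolute angle.** For a normal variable with mean m and SD s, E|X| = s√(2/π)·exp(−m²/2s²) + m(1 − 2Φ(−m/s)). At m = 1.2 this is 4.57 degrees for s = 5.6, 5.67 for s = 7 and 6.45 for s = 8. The two larger SDs are illustrations and do not come from the documents.

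**Illustration 1: equal means, more scatter.** Take both means as 1.2, SDs of 8 (Xpede) and 5.6 (Mendec), and 80 levels per arm treated as independent.

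- SE = √((8² + 5.6²)/80) = √1.192 = 1.09.
- An observed difference of 0 has an upper limit of 1.96 × 1.09 = 2.1, below 2.5, so it passes.
- The mean absolute angle is 6.45 − 4.57 = 1.9 degrees worse.
- With truly equal means, the chance of passing is about Φ(2.5/1.09 − 1.96) = 63%. This outcome is possible, not certain.
- At a test-arm SD of 7, the absolute angle is 5.67 − 4.57 = 1.1 degrees worse.

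**Illustration 2: overshoot.** Take an Xpede mean of −5 against +1.2, with SD 5.6 in both arms. The signed difference is −6.2 and its upper limit is −6.2 + 1.96 × 5.6 × √(2/80) = −4.5, an easy pass. The mean absolute angle rises from 4.57 to 6.14 degrees.

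**The case against.** The strongest reply is that nothing in the documents suggests the two cements would differ in scatter or overshoot. Randomisation is stratified by procedure and number of levels, the model adjusts for baseline angle, and protocol 7.1 shows similar compositions. For balloon kyphoplasty, protocol 4.1 credits angular correction to balloon inflation, which both arms share. Any comparison of means is insensitive to unequal spread, and the SDs of 7 and 8 are assumed. All of this stands, and it limits the point to a gap in what the analysis could detect.

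Three stronger readings are tempting, and the documents do not support them.

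- A reader might take 42% as the share of levels scored wrongly. It is only the share for which a further decrease moves away from zero and still counts as benefit. Much of it is small overshoot, and the figure cannot be fixed until the sign convention is.
- A reader might infer that residual deformity goes unexamined. SAP 7.9.2 and 10.3.1 analyse anterior, mid and posterior height restored, and vertebral compression fracture and adjacent fracture are named adverse events. Collapse could show there. Only an absolute-angle summary is missing.
- A reader might conclude that closer to zero should become the primary rule. Section 9.8 says zero means parallel endplates; it does not say zero is the treatment target. That wording would also not justify the lower-tailed test that is kept.

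**Conclusion.** The point holds as a limitation of the angle co-primary. A one-directional rule on the signed mean cannot separate good correction from offsetting or overshooting deformity, and the planned sensitivity analyses share that blindness. At the planned 6-month values, about 42% of levels would lie on the side where further decrease is credited; the figure is 58.5% under the reversed sign, and about 25% lie more than 2.5 degrees past zero at face value. These shares rest on normality and on the planning mean and SD.

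Harm to the comparison requires the arms to differ in scatter or overshoot. If they did by the amount in the first illustration, a pass could accompany a mean absolute angle 1.9 degrees worse. The second illustration shows the same for overshoot. That the absolute angle measures deformity is inferred from the wedge, fish-mouth and parallel wording, and the sponsor should confirm it. Analysing change from baseline does not alter the direction, because each level's baseline is fixed. The 160 and 200 levels are arithmetically sound.

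**What to change.** 1. Reconcile the sign convention in protocol 9.8, 13.2.1 and 13.2.2, and carry it into SAP 6.2 and 7.9.1.2.
2. Keep the signed co-primary, its margin and its sample size. Limit the smaller-is-better rationale to the kyphotic side of the scale, expressed in the reconciled sign.
3. Add a prespecified sensitivity analysis to SAP 7.9.1.2: the same GEE or mixed model on the absolute core-lab angle at 6 months, with the absolute baseline angle as covariate. If the sponsor confirms a reference value other than zero, use distance from that value.
4. Report the arm difference with its 95% interval beside the co-primary. Do not use 2.5 degrees as a pass rule: it is half of a signed SD of 5.0, whereas the absolute angle has an implied SD of √(1.2² + 5.6² − 4.57²) = 3.45, half of which is about 1.7.
5. State in advance that a worse absolute-angle result will be reported as qualifying any claim of non-inferior angle improvement.

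The cost is one more model on angles already measured and some wording. The downside is one extra result to reconcile in the report.
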